**Table 3-2 Objectives and Endpoints – Expansion Part A (GEN3014 Single Cohorts)**

Objectives	Endpoints
Primary	

 
Assess the preliminary anti-tumor activity of GEN3014
 
	
 
ORR
 

Secondary	

 
Evaluate anti-tumor activity and efficacy of GEN3014
 
	
 
CBR
 
DOR
 
TTR
 
PFS
 
OS
 

 
Evaluate safety of GEN3014
 
	
 
Safety: Incidence and severity of AEs and SAEs, including changes in laboratory values, vital signs, ECGs
 
Immunogenicity: Anti-GEN3014 antibodies
 

 
Characterize the PK of GEN3014
 
	
 
Noncompartmental PK parameters (if feasible): 
 
<math>C_{max}</math>
 
<math>t_{max}</math>
 
<math>C_{trough}</math>
 
<math>AUC_{0-last}</math> and <math>AUC_{0-168h}</math>
 
<math>RA_{Cmax}</math>, <math>RA_{AUC}</math>, and <math>RA_{Ctrough}</math>
 
 
 

Exploratory	

 
Assess potential biomarkers predictive of clinical response to GEN3014 and evaluate potential surrogacy with PFS and OS
 
	
 
CCI
 
CCI
 
CCI
 

 
Assess MRD status
 
	
 
Rate and duration of MRD-negative remission in RRMM, R/R AML, R/R DLBCL
 

 
Explore PK/pharmacodynamic relationship (PK/anti-tumor activity) and PK/safety
 
	
 
Dose concentration response (biomarkers and/or efficacy, safety) relationship
 

 
Evaluate the pharmacodynamic profiles of GEN3014
 
	
 
Pharmacodynamic markers in blood and tumor samples, including frequencies of NK cells and other leukocyte subsets, and complement analyses
 

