### 5.1.2 Visit Windows

Any efficacy analysis that utilizes time to event approach will be based on an exact determination of time from C1D1 to the date of event/censoring.

Unless otherwise stated data will be presented as collected on the nominal visits, that is, if data are collected as part of CxDy visit in the CRF it will be presented as such in analyses irrespective of the subject's adherence to the protocol visit schedule and actual collection date. Unscheduled visits will not be displayed summaries but will be listed.

Disease assessments are not tied to nominal visits in eCRF but are scheduled to be performed on a regular basis per protocol. The analysis time window listed in Table 4 and Table 5 will be used to slot actual disease assessment date into planned disease assessment schedules for summary statistics for RRMM, AML and R/R DLBCL, respectively. The visit window is mainly for display disease assessment in a chronological order and will generally not be used in actual analysis.

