#### **5.4.5 PFS**

Progression-free survival (PFS, months) is defined as the time from C1D1, or randomization, to first documented PD or death due to any cause, whichever occurs earlier (see Table 8 for censoring rules). PFS will be derived for all subjects and analyzed using similar methods as DOR.

PFS event-free rate at a landmark time T is defined as the probability that a subject has not progressed and is alive at time T. (Subjects with an intermittent event prior to the landmark will not be a part of the analysis.) PFS event-free rates at 6, 9, and 12 months (or later times if available) will be presented along with 95% CI.

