#### **5.4.6 OS**

Overall survival (OS, months) is defined as time from C1D1, or randomization, to death due to any cause, will be analyzed using the Kaplan-Meier method. The subjects who are alive or with no observed death will be censored at last contact date.

Median OS with associated 95% CI as well as first and third quartiles and range will be provided. Survival rates at 6, 9 and 12 months (or later times if available) will be presented along with 95% CI.

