#### **5.6.4 Rate of MRD Negativity and Duration of MRD Negativity**

Minimal residual disease (MRD) negativity is defined as no malignant clone sequence being detected at a given threshold in PBMCs or ctDNA (e.g. for  $10^{-5}$ , the clone sequence is not detected in the background of 100,000 nucleated cells). For evaluation of MRD negativity rate, subjects are considered MRD negative if there is at least one on-treatment MRD negative whole blood sample; all remaining subjects in the analysis set are considered MRD positive (e.g. those who only have MRD positive test results or those who have no MRD assessment data). Duration of MRD negativity is defined as the number of days from the first documentation of MRD- to the date of MRD status change (not MRD-). The primary MRD- threshold is selected as of  $10^{-5}$ . Other thresholds, including  $10^{-4}$  and  $10^{-6}$ , may also be explored.

MRD- rate analyses will be performed in a similar manner as for ORR, and duration of MRD- analyses will be conducted in similar methods for DOR.

PFS and OS analysis by MRD negativity status may be performed to assess the relationship between MRD negativity status and PFS/OS as part of exploratory analyses.

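### PFS and OS by MRD status (SAP 5.6.4) group subjects by a later on-treatment result but start the clock at C1D1 or randomization, which favours MRD-negative subjects even with no true association

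*SAP*

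**What the plan says.** SAP 5.6.4 gives one subject-level definition: "subjects are considered MRD negative if there is at least one on-treatment MRD negative whole blood sample". Everyone else is counted as MRD positive, for example "those who only have MRD positive test results or those who have no MRD assessment data". The section then states that "PFS and OS analysis by MRD negativity status may be performed to assess the relationship between MRD negativity status and PFS/OS". It labels this analysis exploratory and gives no other grouping rule, time origin or model.

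The clocks are set elsewhere:

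- SAP 5.4.5: "Progression-free survival (PFS, months) is defined as the time from C1D1, or randomization, to first documented PD or death due to any cause".
- SAP 5.4.6: OS "is defined as time from C1D1, or randomization, to death due to any cause".
- SAP 5.1.2: any time-to-event efficacy analysis "will be based on an exact determination of time from C1D1 to the date of event/censoring".
- SAP 5.1.1.2: the on-treatment period begins at first dose, so a qualifying sample comes after that point.

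The sampling schedules are in the protocol. For DLBCL (Table 1-11), whole blood is taken on Day 1 of Cycles 1, 3, 5, 7 and 10, then every 6 months from Cycle 13. For RRMM (Tables 1-4, 1-9 and 1-15), post-baseline samples are taken only at CR/sCR and then at 6, 12, 18, 24 and 30 months in subjects who reached CR/sCR and remain on trial.

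Neither document mentions an MRD landmark or a time-dependent covariate. The landmark text in SAP 5.4.5 concerns event-free rates at 6, 9 and 12 months, not grouping by MRD.

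**The concern.** A Kaplan-Meier comparison from time zero assumes that group membership is known at time zero. Here it is decided by something that happens later, and only to subjects who are still progression-free and on trial when a sample is due. The interval from C1D1 to the first negative sample is therefore event-free by construction in the negative group. Early progressors and early deaths go to the positive group whatever their MRD status would have been, and counting untested subjects as positive adds to this. It is the usual immortal-time (guarantee-time) bias.

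At stake is one exploratory reading: whether MRD negativity goes with longer PFS or OS under these treatments. Done this way, the analysis would tend to support that association whether or not it exists.

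**Working it through.** The documents give no planned figure for this analysis, so there is none to reproduce. The check asks what the rule produces when MRD is unrelated to PFS.

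**Inputs from the documents.** The MRD rule (SAP 5.6.4), the time origin (SAP 5.4.5, 5.4.6), the DLBCL blood schedule (Protocol Table 1-11) and N=40 (DLBCL maximum, SAP 3). C3D1 is 56 days after C1D1, and 56 / 30.4375 = 1.84 months. C5D1 is 112 days after C1D1, or 3.68 months.

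**Assumptions, not in the documents.** Exponential PFS with median 4 months; MRD independent of PFS; samples taken only while progression-free; C3D1 as the first qualifying sample.

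**Step 1. Stable trait, closed form.** Let a fraction q of subjects carry an MRD-negative trait that is detectable from C3D1 and unrelated to PFS.

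- Share with an event before C3D1: 1 − 2^(−1.84/4) = 0.273. All of them are counted positive.
- Negative group: carriers still progression-free at 1.84 months. With a constant hazard, their median PFS from C1D1 is 1.84 + 4 = 5.84 months for every q.
- Positive group: all non-carriers plus the carriers with an early event. Its median t solves 2^(−t/4) = (1 − q + 0.273q) / (2(1 − q)).

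| q | right-hand side | median PFS, positive | median PFS, negative |
|---|---|---|---|
| 0.1 | 0.9273 / 1.8 = 0.515 | 3.83 | 5.84 |
| 0.2 | 0.8546 / 1.6 = 0.534 | 3.62 | 5.84 |
| 0.3 | 0.7819 / 1.4 = 0.559 | 3.36 | 5.84 |
| 0.5 | 0.6365 / 1.0 = 0.637 | 2.61 | 5.84 |

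The true median is 4 months in everyone, so the gap of 2.0 to 3.2 months comes from the grouping alone.

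**Step 2. False-positive yardstick by simulation.** N=40, administrative censoring uniform on 6 to 24 months, two-sided 5% log-rank test from C1D1.

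| MRD model | setting | rejection |
|---|---|---|
| Stable trait | prevalence 0.1 / 0.2 / 0.3 / 0.5 | about 3% / 7% / 14% / 34% |
| Redrawn at each sample | probability 0.1 / 0.2 / 0.3 | about 42% / 80% / 96% |

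The low rates at prevalence 0.1 and 0.2 reflect a small negative group. Step 1 shows that the curves are still displaced.

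**Step 3. Hazard ratios under the redrawn model.** These runs used median PFS of 2, 4, 6 or 12 months, negativity probability 0.1 or 0.3, cutoff at 24 months and median post-progression survival of 6 months. They covered the DLBCL schedule and a fixed-time stand-in for RRMM sampling, 16 scenarios in all, with a true hazard ratio of 1.

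- Grouped as in SAP 5.6.4: PFS HR 0.26 to 0.51, OS HR 0.31 to 0.73.
- MRD as a time-dependent covariate: PFS HR 0.94 to 1.06.
- 6-month landmark in progression-free subjects: PFS HR 0.96 to 1.11, OS HR 0.89 to 1.18. Log-rank rejection at N=40 was 5% to 11%, the upper end where few subjects remained at risk.

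In the stable-trait model a landmark removes the bias exactly: from 3.68 months onward, remaining PFS has median 4 months in both groups.

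**The case against.** **The reading is an inference.** The ever-negative rule is written for the MRD rate, and the PFS/OS sentence sets no grouping rule of its own. That is true. But it is the only subject-level status defined, and the next use of MRD negativity status naturally picks it up. If something else is meant, the SAP has to say so, and the remedy is the same.

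**No log-rank test is planned.** Also true. The SAP has no hypotheses, and time-to-event output is Kaplan-Meier estimates with confidence intervals. The rejection rates are only a yardstick; the displaced curves in step 1 do not depend on a test.

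**The size is not established.** This stands in full. A reader might infer that the analysis is bound to show a large advantage. Rates of 42% to 96% arise only if status is redrawn at each visit, which gives long survivors repeated chances to turn negative. The hazard ratios in step 3 share that assumption. A DLBCL Cycle 1 Day 1 (+2 days) sample might also count as on-treatment with almost no delay.

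**Three wider readings are tempting but unsupported.**

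- AML: Protocol Table 1-10 schedules MRD on bone marrow only, while the SAP rule requires whole blood. Under the rule as written, no scheduled AML sample could make a subject negative, so no AML figure can be attached to it.
- Surrogacy: the objective to "evaluate potential surrogacy with PFS and OS" belongs to the predictive-biomarker row of Protocol Table 3-2. MRD is a separate row with rate and duration as its endpoints.
- ADA: SAP 5.6.3 sets subjects without a post-baseline assessment to missing rather than negative, so the same argument does not carry over.

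**Conclusion.** The concern holds for the optional PFS/OS analysis by MRD status in SAP 5.6.4. Followed as written, it favours MRD-negative subjects even with no true association. The direction follows from the definitions alone.

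The size rests on assumptions about PFS and about how MRD behaves over time. For the DLBCL schedule with median PFS 4 months and N=40, the yardstick rejection rate runs from about 3% to 34% under a stable trait, and from about 42% to 96% under per-sample redraws. The documents do not say which model is closer, so no single figure should be quoted as the expected bias.

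Part B counts from randomization rather than C1D1, which changes nothing in the argument. No primary or secondary endpoint, interim rule or decision is affected.

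**What to change.** Replace the PFS/OS sentence in SAP 5.6.4 with text stating that any PFS or OS analysis by MRD status will use one of two methods:

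- MRD negativity as a time-dependent covariate; or
- a disease-specific landmark matched to the sampling schedule, for example just after C5D1 for DLBCL and no earlier than the 6-month sample for RRMM. It includes only subjects alive, progression-free and in follow-up at the landmark, for OS as well as PFS, grouped on MRD results up to that point.

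Subjects without an MRD result by then should be shown separately, not counted as positive. An early landmark such as C5D1 does not suit RRMM, where sampling waits for CR/sCR. The time-dependent model was checked here for PFS only. For OS the progression-free landmark is safer, because negativity can in practice be acquired only before progression.

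The cost is SAP wording and minor programming, with no new data. Subjects with an event before the landmark leave this one analysis. At median PFS 4 months about 40 × 2^(−3.68/4) = 21 of 40 remain at C5D1, so the result will be imprecise and should be reported as such.

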#### **5.6.5 Subgroup Analyses**

Due to the heterogeneous population, and expected low sample size within each disease type, there are no subgroup analyses planned for the escalation stage.

### **5.7 Interim Analyses**

#### **5.7.1 Expansion Part A – Anti-CD38 mAb-Naive RRMM Cohort**

Data from the initial 10 anti-CD38 mAb-naive RRMM subjects belonging to the RES who received GEN3014 (at 16 mg/kg) from the Dose Escalation and/or from the Expansion Part A, will be reviewed by the Safety Committee and DMC when they have completed  $\geq 2$  cycles of treatment. If 2 or more out of the initial 10 subjects respond to GEN3014, the comparison vs daratumumab SC in Expansion Part B will be initiated.

Should the true underlying response rate be 40%, the probability to have 2 or more responders in 10 subjects is 95%. That is, it would be very unlikely to have 0 or 1 responders (in 10 evaluated) under the assumption of a response rate of 40%.

#### **5.7.2 Expansion Part A – R/R DLBCL Cohort**

The maximum sample size in the R/R DLBCL expansion cohort is set to 40 subjects. In order not to expose R/R DLBCL subjects to a potentially non-efficacious GEN3014 RP2D dose, an ongoing and non-binding interim futility analysis will be conducted based on the response data from the

initial 20 subjects belonging to the RES. The timing of the interim analysis is when the initial 20 subjects have completed  $\geq 2$  cycles of GEN3014 treatment. The totality of the data (including efficacy, safety, and PK) will be evaluated by the sponsor Safety Committee, which decides if enrolment should be stopped or continued.

The SADAL trial reported an ORR of 28% (36/127; 95% CI 20.7-37.0) (Kalakonda et al., 2020) which led to approval of XPOVIO in R/R DLBCL subjects. For the purpose of signal finding in heavily pre-treated DLBCL subjects the undesirable response rate for GEN3014 is set to 20% and the desirable response rate is set to 40%. With a Simon's 2-stage design (with type I error rate of 4.04% and power of 85.39%) at least 5/20 responders are needed to pass the futility bar. At least 13/40 responders are needed to consider GEN3014 having a potential in DLBCL who have exhausted SOC.

### 5.7.3 Safety Stopping Guidance for Expansion Cohorts

Pocock's flexible alpha-spending method will be used as a stopping guidance for each expansion cohort (Ivanova et al., 2005). For each individual cohort, the overall significance level to stop further treatment due to safety concern is set to 5%. Table 5-7 through Table 5-10 provide stopping guidance for the different disease cohorts treated with GEN3014 in expansion (does not include subjects treated with daratumumab SC). (The nominal P values will be adjusted if the information rates deviate from the planned.)

For the grade 4 treatment-related AEs, the same acceptable rate of 10% is adopted for all expansion cohorts. Treatment-related deaths may occur with a slightly higher rate in the AML cohort as compared to the MM and DLBCL cohorts. For AML, if data indicate a treatment-related death rate exceeding 5%, stopping the expansion cohort will be considered. For MM and DLBCL, if data indicate a treatment-related death rate exceeding 1%, stopping the expansion cohort will be considered.

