**Table 9-2 Stopping Guidance for RRMM anti-CD38 mAb-naïve**

	n=5	n=10	n=20	n=35	n=50
Grade $\geq 4$ Treatment-Related AE (stop if $\geq$ )	4	4	6	8	10
Treatment-Related Death (stop if $\geq$ )	2	2	2	3	3

AE=adverse event; CD=cluster of differentiation; mAb=monoclonal antibody; RRMM=relapsed or refractory multiple myeloma.

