**Table 9-3 Stopping Guidance for RRMM anti-CD38 mAb-refractory**

	n=5	n=10	n=20
Grade $\geq 4$ Treatment-Related AE (stop if $\geq$ )	3	4	6
Treatment-Related Death (stop if $\geq$ )	2	2	2

AE=adverse event; CD=cluster of differentiation; mAb=monoclonal antibody; RRMM=relapsed or refractory multiple myeloma.

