**Table 5-10 Stopping Guidance for RRMM anti-CD38 mAb-naive**

	n=5	n=10	n=20	n=35	n=50
Grade $\geq 4$ Treatment-Related AE	4	4	6	8	10
Treatment-Related Death	3	3	4	6	7

AE=adverse event; CD=cluster of differentiation; mAb=monoclonal antibody; RRMM=relapsed or refractory multiple myeloma.

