**Table 5-11 Stopping Guidance for RRMM anti-CD38 mAb-refractory**

	n=5	n=10	n=20
Grade $\geq 4$ Treatment-Related AE	3	4	6
Treatment-Related Death	3	3	4

AE=adverse event; CD=cluster of differentiation; mAb=monoclonal antibody; RRMM=relapsed or refractory multiple myeloma.

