**Table 5-12 Stopping Guidance for R/R DLBCL**

	n=5	n=10	n=20	n=40
Grade $\geq 4$ Treatment-Related AE	3	4	6	9

Treatment-Related Death	2	2	2	3
-------------------------	---	---	---	---

AE=adverse event; R/R DLBCL=relapsed or refractory diffuse large B-cell lymphoma.

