**Table 5-13 Stopping Guidance for R/R AML**

	n=5	n=10	n=20
Grade $\geq$ 4 Treatment-Related AE	3	4	6
Treatment-Related Death	2	3	4

AE=adverse event; R/R AML=relapsed or refractory acute myeloid leukemia.

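### The myeloma treatment-related-death boundaries in SAP Tables 5-10 and 5-11 do not follow from the stated 1% rate and 5% level, and they conflict with the SAP's own DLBCL row

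*SAP*

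**What the plan says.** SAP 5.7.3 describes a Pocock-type alpha-spending guide, applied separately to each expansion cohort. On the level it says: "For each individual cohort, the overall significance level to stop further treatment due to safety concern is set to 5"%. The acceptable rate of grade 4 treatment-related events is 10% in all cohorts. For treatment-related deaths, AML has 5%, and the other two diseases share one figure: "For MM and DLBCL, if data indicate a treatment-related death rate exceeding 1%, stopping the expansion cohort will be considered". Protocol 9.6 states the same 5% level and the same death rates.

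The printed treatment-related-death rows are:

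| Cohort (stated rate) | Looks, n | SAP | Protocol v8.0 |
|---|---|---|---|
| Myeloma, naive (1%) | 5/10/20/35/50 | 3/3/4/6/7 | 2/2/2/3/3 |
| Myeloma, refractory (1%) | 5/10/20 | 3/3/4 | 2/2/2 |
| DLBCL (1%) | 5/10/20/40 | 2/2/2/3 | 2/2/2/3 |
| AML (5%) | 5/10/20 | 2/3/4 | 2/3/4 |

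The SAP rows are in "Table 5-10 Stopping Guidance for RRMM anti-CD38 mAb-naive", "Table 5-11 Stopping Guidance for RRMM anti-CD38 mAb-refractory", "Table 5-12 Stopping Guidance for R/R DLBCL" and "Table 5-13 Stopping Guidance for R/R AML". The protocol's myeloma rows are in "Table 9-2 Stopping Guidance for RRMM anti-CD38" (naive) and "Table 9-3 Stopping Guidance for RRMM anti-CD38 mAb-refractory". All four grade ≥4 rows agree between the documents, so six of the eight rows match and only the two myeloma death rows differ. SAP Appendix 1 records no changes to protocol-planned analyses.

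**The concern.** Myeloma and DLBCL share one rate and one overall level, yet at n=5/10/20 both myeloma tables require 3/3/4 deaths and the DLBCL table requires 2/2/2. The different maximum sample sizes do not explain this. The refractory cohort (maximum 20) and the naive cohort (maximum 50) both print 3/3/4, while DLBCL, whose maximum of 40 lies between them, prints 2/2/2.

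What is at stake is when fatal toxicity would trigger a formal review. Under the SAP rows, four related deaths rather than two are needed at n=20, and seven rather than three at n=50. Anyone using the SAP tables would be working to a tolerance well above the 1% that the text states.

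**Working it through.** **Inputs.** From SAP 5.7.3 and its tables: overall level 0.05 per cohort; death rate p = 0.01 for myeloma and DLBCL; grade ≥4 rate p = 0.10; and the looks shown above.

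**Method.** The SAP names the spending family but does not print the function. I used the usual Pocock-type form, cumulative spend α(t) = 0.05·ln(1 + (e − 1)t) with t = n/N. At each look the boundary is the smallest count for which the exact cumulative binomial probability of crossing, at this or any earlier look, is at or below α(t).

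**Reproducing the plan's own figures first.**
- Grade ≥4 rows at p = 0.10: 4/4/6/8/10 (naive), 3/4/6 (refractory), 3/4/6/9 (DLBCL) and 3/4/6 (AML). All four are as printed.
- DLBCL death row at p = 0.01: 2/2/2/3, as printed, with total crossing probability 2.05%.

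**Myeloma naive deaths at p = 0.01.**

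| n | α(t) | Boundary | Cumulative crossing | SAP prints |
|---|---|---|---|---|
| 5 | 0.79% | 2 | 0.10% | 3 |
| 10 | 1.48% | 2 | 0.43% | 3 |
| 20 | 2.62% | 2 | 1.69% | 4 |
| 35 | 3.95% | 3 | 1.88% | 6 |
| 50 | 5.00% | 3 | 2.55% | 7 |

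**Myeloma refractory deaths at p = 0.01.** The spend is 1.79%, 3.10% and 5.00%. The boundaries are 2/2/2, with total crossing probability 1.69%. The SAP prints 3/3/4.

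Both derived rows equal protocol Tables 9-2 and 9-3.

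**Level that the SAP rows actually attain.** At p = 0.01, the total crossing probability is 0.014% for both 3/3/4/6/7 and 3/3/4, against the 5% specified.

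**Where the SAP rows come from.** The same rule at p = 0.05 returns 3/3/4/6/7 (total 3.11%) and 3/3/4 (total 2.22%), exactly as printed. Under this rule the printed rows arise only for p of about 5.0–5.25% (naive) and 4.45–6.55% (refractory).

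**Sensitivity to the unstated convention, p = 0.01.**

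| Convention | Naive |
|---|---|
| Pocock-type spend, 2.5% | 2/2/3/3/3 |
| Pocock-type spend, 5% | 2/2/2/3/3 |
| Pocock-type spend, 10% | 2/2/2/2/2 |
| Linear spend, 5% | 2/2/2/3/3 |
| Constant nominal level, total ≤5% | 2/2/2/3/3 |

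The refractory row is 2/2/2 under all five. None of them gives the SAP rows, which are higher at every look.

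**Chance of crossing.** The documents give no expected death rate, so the true rates below are assumptions.

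| True death rate | Naive: SAP rows / 1% rows | Refractory: SAP rows / 1% rows |
|---|---|---|
| 2% | 0.13% / 10.7% | 0.13% / 6.0% |
| 3% | 0.5% / 22.9% | 0.5% / 12.0% |
| 5% | 3.1% / 50% | 2.2% / 26% |

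The true rate at which the chance of crossing reaches 5% is 5.7% (SAP) against 1.4% for the naive cohort, and 6.6% against 1.8% for the refractory cohort.

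**A row that does not reproduce.** The AML death row 2/3/4 is not returned at 5% by the spending rule, which gives 3/3/4. A constant-nominal rule does return it (total 3.7%), but that rule gives 3 instead of the printed 4 at n=5 in the naive grade ≥4 row. I therefore place no weight on comparisons with AML.

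**The case against.** The strongest objection is that the SAP tables do not govern conduct. Protocol 6.6.2 sends the reader to protocol 9.6 for expansion stopping criteria, and 9.6 already prints 2/2/2/3/3 and 2/2/2. The tables are guidance, since stopping is only to be considered. The DMC reviews all safety information, and protocol 10.1.7 lets the Safety Committee stop enrollment on benefit/risk. No endpoint, estimate or analysis set is affected. The SAP is also version 1, written to protocol v5.0, whose tables are not supplied, so it may simply have copied an older table that a rebase to v8.0 would overwrite.

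Most of this stands, and it limits the consequence. It does not remove the error. Protocol 6.6.2 does not say which table the DMC and Safety Committee work from, and the DMC charter is not among the documents. Version lag could explain the difference from protocol v8.0. It cannot explain why two diseases with the same stated rate and level have different boundaries inside the SAP.

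A further fair point is that rare crossing at a true rate of 1% is desirable, so a low crossing probability there is no harm in itself. The loss lies at true rates above 1%.

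**Conclusion.** The concern holds, with high confidence. The two myeloma death rows in the SAP do not follow from its stated 1% rate and 5% level, and they contradict its DLBCL row at the same rate. They fit a 5% death rate. At assumed true rates of 2–5%, they lower the chance of crossing from 10.7–50% to 0.13–3.1% (naive) and from 6.0–26% to 0.13–2.2% (refractory).

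The derived boundaries rest on a spending formula that the SAP does not print. That reading is supported by the five SAP rows it reproduces and by the protocol's own myeloma rows. The conflict with DLBCL rests on no formula. This should be fixed, but it is a correction to monitoring guidance and leaves the efficacy analyses untouched.

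**What to change.** Replace the treatment-related-death row in SAP Table 5-10 with 2/2/2/3/3 and in Table 5-11 with 2/2/2. Label the boundaries as *stop if ≥*, as the protocol tables do; the SAP tables carry no such label. Confirm with the DMC and the Safety Committee that they work from the protocol v8.0 boundaries. One editorial correction belongs here too: the text of SAP 5.7.3 refers to Tables 5-7 to 5-10, but the tables are numbered 5-10 to 5-13.

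The cost is two table rows, a label, a cross-reference and one confirmation, with no added patients and no protocol change. Rebasing the SAP from protocol v5.0 to v8.0 is a separate task and this correction need not wait for it.
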